6.4 Protocol Therapy Discontinuation

In addition to discontinuation from therapy related to toxicities outlined above, a subject will also be discontinued from protocol therapy and followed per protocol under the following circumstances outlined below. The reason for discontinuation of protocol therapy will be documented on the electronic case report form (eCRF).

- Intercurrent illness or SAE that prevents further administration of treatment
- Noncompliance with treatment plan
- Site investigator determines a change of therapy would be in the best interest of the subject
- Protocol violation - any patient found to have entered this study in violation of the protocol might be discontinued from the study at the discretion of the sponsor-investigator
- Subject requests to discontinue protocol therapy, whether due to unacceptable toxicity or for other reasons
 - In a subject decides to prematurely discontinue protocol therapy (“refuses treatment”), the subject should be asked if he or she may still be contacted for further scheduled study assessments. The outcome of that discussion should be documented in both the medical records and in the eCRF.
- Female subject becomes pregnant

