Creatinine OR Calculated Creatinine Clearance ¹	< 1.5x ULN OR $\geq 60 \text{ mL/min}$ for participants with creatinine levels $> 1.5x \text{ ULN}$
Hepatic	
Total Bilirubin	$\leq 1.5 \times \text{ upper limit of normal (ULN)}^2$
Aspartate aminotransferase (AST)	$\leq 5 \times \text{ ULN}$; given presence of liver metastases
Alanine aminotransferase (ALT)	$\leq 5 \times \text{ ULN}$; given presence of liver metastases
Alkaline Phosphatase	$< 2.5 \times \text{ ULN}$
Coagulation	
International Normalized Ratio (INR) or prothrombin time (PT) or activated partial thromboplastin time (aPTT)	$\leq 1.5 \times \text{ ULN}$ unless participant is receiving anticoagulant therapy, in which case they must be on a stable dose

¹Cockcroft-Gault formula will be used to calculate creatinine clearance

²If patient has conditions of congenital hyperbilirubinemia, then patient must have isolated hyperbilirubinemia (e.g. no other liver function test abnormalities) with maximum bilirubin $< 2 \times$ institutional ULN

9. Females of childbearing potential must have a negative serum pregnancy test within 24 hours of study drug. **NOTE:** Females are considered of childbearing potential unless they are surgically sterile (have undergone a hysterectomy, bilateral tubal ligation, or bilateral oophorectomy) or they are naturally postmenopausal for at least 12 consecutive months without another cause, or a documented serum follicle stimulating hormone (FSH) ≥ 35 mIU/mL. Should a woman become pregnant or suspect she is pregnant while participating in this study, she should inform her treating physician immediately.
10. Females of childbearing potential and male participants must be willing to abstain from heterosexual intercourse or to use contraception as outlined in Section 5.6.
11. As determined by the enrolling physician or protocol designee, ability of the subject to understand and comply with study procedures for the entire length of the study.

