12.4 Analysis Datasets

Population	Definition
Enrolled	This will comprise all subjects who meet the eligibility criteria and are registered onto the study.
Per Protocol Set (Valid Cases, Efficacy Sample, Evaluable Subjects Sample)	This will comprise all subjects who complied with the protocol sufficiently to ensure that these data would be likely to exhibit the effects of treatment, according to the underlying scientific model. Compliance covers such considerations as exposure to treatment, availability of measurements and absence of major protocol violations. This population should be specifically defined in the protocol.
Treated	This will comprise all subjects who have been exposed to the planned course of treatment to any extent.

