12.6 Assessment of Efficacy

All patients who receive one dose of protocol therapy and are completely resected (rendered NED) will be evaluable for assessment of efficacy.

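### Section 6.4 both keeps protocol violators in follow-up and lets the sponsor-investigator take them off the study, and no analysis set holds every randomised patient

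*Combined protocol and SAP*

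**What the plan says.** Section 6.4 (Protocol Therapy Discontinuation) opens by stating that, besides toxicity, "a subject will also be discontinued from protocol therapy and followed per protocol under the following circumstances outlined below". The fourth bullet under that lead-in, on protocol violations, says something different: a patient "found to have entered this study in violation of the protocol might be discontinued from the study at the discretion of the sponsor-investigator".

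Section 6.5 deals with leaving the protocol altogether and asks for assessments to be completed as fully as possible. It applies when the subject decides to leave.

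Section 12.4 defines three sets:
- Enrolled: "This will comprise all subjects who meet the eligibility criteria and are registered onto the study".
- Treated: "This will comprise all subjects who have been exposed to the planned course of treatment to any extent".
- Per Protocol: conditions that include exposure to treatment and "absence of major protocol violations", with the exact definition left to be supplied.

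Section 12.6 defines the efficacy population without using these labels: "All patients who receive one dose of protocol therapy and are completely resected (rendered NED) will be evaluable for assessment of efficacy". Section 12.7 estimates survival in patients with complete resection. Section 2.2 lists a comparison of 3-year OS from registration and names no analysis set for it.

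**The concern.** Stopping treatment and leaving the study are different events, and the protocol usually separates them. Sections 5.1.3 and 5.1.5 both take patients off protocol therapy while keeping them in follow-up, and 6.5 draws the same distinction. Against that background the violation bullet reads as permission to take a patient off the study. The permission is optional, rests with one party and has no time limit. Only Arm B receives vaccine and the Day -28 and Day -14 visits, so the arm is visible when the choice is made, and the patient's course may be known too.

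If the bullet is followed rather than the lead-in, a resected patient could stay in the efficacy population with no later survival status recorded. Separately, a randomised patient later found ineligible falls outside Enrolled as it is literally defined. If that set were used for OS from registration, the comparison would no longer cover the randomised groups. With 22 deaths expected (section 12.8), a few deaths lost in one direction could matter.

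**Working it through.** **1. The passages side by side.** The lead-in says off therapy, and followed. The bullet says possibly off the study, at the sponsor-investigator's discretion. Section 6.5 protects data after a subject's own decision only. The study calendar lists survival status under follow-up but does not mention a patient removed by the sponsor-investigator. Whether such a patient is followed therefore depends on which half of 6.4 a site applies.

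**2. Who is in which set.** A randomised patient found ineligible is not in Enrolled. If dosed, the patient is in Treated; if also completely resected, in the 12.6 population. If never dosed, the patient is in none of the three sets in 12.4. No set equals all randomised patients.

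**3. The plan's own figures.** Section 12.3 gives 35 resected patients per arm, 3-year OS of 58.8% v 88.7%, a one-sided 2.5% log-rank test and 80% power.
- Under exponential survival, HR = ln(0.887)/ln(0.588) = 0.226.
- Freedman's formula: deaths = (1.960 + 0.842)² × [(1 + 0.226)/(1 - 0.226)]² ≈ 19.7, rounded up to 20, against 22 expected in section 12.8.
- Deaths with exactly 3 years each: 35 × 0.412 + 35 × 0.113 = 18.4. With 12-month uniform accrual and 3 years after the last patient: 20.7. Freedman power is 77% and 82% respectively.
- 70/0.95 = 73.7, rounded up to 74.

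The plan's size and power reproduce.

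**4. Non-selective loss.** The number of patients found ineligible is not in the documents, so the numbers removed are assumptions. Simulation: 35 per arm, exponential survival, one-sided 2.5% log-rank, no interim look, 20,000 trials per case.
- Power under the planned effect after losing 2, 4 or 6 patients at random: from 84.5% to 82.7%, 82.2% and 80.7% (3 years each), or from 88.5% to 87.4%, 86.4% and 85.5% (3 to 4 years).
- Type I error at 58.8% in both arms and 3 to 4 years, after removing 1, 2 or 3 Arm B patients regardless of outcome: 2.4%, 2.5% and 2.6%.
- Type I error after censoring three random Arm B patients in the first 6 months: 2.4%.

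**5. Worst-case selective loss.** There is no true difference, and 1, 2 or 3 Arm B patients who died are deleted. The 73.75% setting is the mean of 58.8% and 88.7%, chosen because it gives a death count near the plan's 22.

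| 3-year OS, both arms | Follow-up | Mean deaths before deletion | None deleted | 1 | 2 | 3 |
|---|---|---|---|---|---|---|
| 58.8% | 3 to 4 years | 32 | 2.4% | 3.5% | 4.7% | 6.6% |
| 58.8% | 3 years | 29 | 2.5% | 3.7% | 5.2% | 7.7% |
| 73.75% | 3 to 4 years | 21 | 2.5% | 4.2% | 6.4% | 10.0% |
| 73.75% | 3 years | 18 | 2.4% | 4.3% | 7.3% | 11.9% |

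Repeat runs at 3 to 4 years gave 3.2-3.7%, 4.4-4.9% and 6.5-7.1% in the first setting, and 3.9-4.2%, 6.4-6.8% and 10.0-10.6% in the third.

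**The case against.** The strongest reply is that the bullet sits in a section on stopping therapy, under a lead-in that keeps these patients in follow-up, so the text is only loosely worded. A reader might infer that the rule ends collection of the death date. The documents do not say that; they contradict themselves and leave the matter open. This part of the reply stands.

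A reader might also infer that patients outside Enrolled drop out of the primary analysis. They do not: sections 12.6 and 12.7 have no eligibility condition, and no analysis is assigned to Enrolled.

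A third tempting inference is that the pregnancy test tied to study drug shows that eligibility is settled only after randomisation. It does not. Five business days is the maximum interval from randomisation to therapy, so the test can come first, and an undosed patient is outside 12.6 in any case.

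The simulation is open to challenge too. It deletes patients who died, whereas the bullet speaks of discontinuing a patient, and nothing authorises erasing a recorded death. Early removal would normally censor later follow-up, and the effect appears only when loss depends on both arm and outcome. This is correct, and it is why the figures are a bound and not a forecast.

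Safeguards exist. The bullet concerns violations at entry, the reason for discontinuation goes on the eCRF, and the data safety monitoring committee receives protocol deviations and reviews study data quarterly. They reduce the scope for unseen selection. They do not require survival status to be collected after a removal.

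**Conclusion.** The point holds as an inconsistency in 6.4 combined with a gap in 12.4. The plan permits a discretionary removal from the study, without time limit and with the arm visible, and does not secure survival data afterwards. It also lacks a set containing every randomised patient, which matters for OS from registration if Enrolled is the set chosen.

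The size depends wholly on how removals occur. Random removals leave type I error at about 2.5% and cost little power. Selective loss of one to three Arm B deaths raises type I error to about 3-7% with 58.8% OS in both arms (about 32 deaths), or 4-11% at about 21 deaths; with exactly 3 years of follow-up the upper ends reach about 8% and 12%. These figures assume exponential survival, 35 per arm, no interim look and deletions all in one direction. The count of one to three is an assumption. The documents do not show that selective removal is likely, and the primary analysis as written does not exclude ineligible patients.

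**What to change.** - Reconcile the violation bullet in 6.4 with its lead-in. Whether and when treatment stops is for the investigators to settle; the statistical need concerns follow-up only.
- State that survival and recurrence follow-up continues for every randomised patient, whatever the violation, unless consent is withdrawn, and that no patient is dropped from an efficacy analysis for ineligibility found after randomisation.
- In 12.4, define an all-randomised set analysed by assigned arm, by removing the eligibility condition from Enrolled and referring to randomisation. Name it as the set for OS from registration.
- Confine eligibility exclusions to the Per Protocol set, judged on facts that predate randomisation and without knowledge of outcome.

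The cost is a few wording changes and continued follow-up of a small number of patients. A few ineligible patients will remain in the analyses and slightly dilute the effect. No change in sample size follows.

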6.5 Protocol Discontinuation

If a subject decides to discontinue from the protocol (and not just from protocol therapy) all efforts should be made to complete and report study assessments as thoroughly as possible. A complete final evaluation at the time of the subject's protocol withdrawal should be made with an explanation of why the subject is withdrawing from the protocol. If the reason for removal of a subject from the study is an adverse event, it will be recorded on the eCRF.

7. STUDY CALENDAR & EVALUATIONS

1 cycle = 14 days during neoadjuvant and adjuvant treatment 1 cycle = 28 days during maintenance treatment A = Arm A and B = Arm B	Screen	Arm B ± 2 days		Neoadjuvant Therapy C1- C4	Pre-Surgery	Surgery or Biopsy	Adjuvant Therapy C5-C12 ⁷	Maintenance C13-36 ¹¹	Safety Visits D30/D100 ¹²	Follow up ¹³
	D-28	D-28	D-14	± 2 days			± 2 days	D1 ± 2 days	+7 days	± 14 days
REQUIRED ASSESSMENTS										
Informed Consent	X									
Medical History including smoking history ¹	X									
Physical Exam ²	X	B	B	X	X		X ²	X	D30	X
Vital signs ECOG Performance Status ²	X	B	B	X	X		X	X	D30	X
ECG	X				X		C5D1			
AEs & concomitant medications	X	B	B	X	X		X	X	X	X
LABORATORY ASSESSMENTS										
Complete Blood Cell Count with diff (CBC)	X	B	B	X	X		X	X	D30	
Comprehensive Metabolic Profile (CMP)	X	B	B	X	X		X	X	D30	
CEA and CA19-9 ³	X				X		C8D1	X ¹¹		X ¹²
PT/INR and aPTT ⁴	X				X					
Thyroid Function ⁴	X	B		X	X		X ⁴	X ⁴		
Amylase & Lipase ⁴	X	B	B	X			X ⁴	X ⁴		
Pregnancy test (serum or urine) (WOCBP) ⁵	X ⁵	B	B	X ⁵			X ⁵	X ⁵		
DISEASE ASSESSMENT										
CXR ¹⁰					X					
CT or PET of chest ⁶	X				X ⁶		X ⁶	X ⁶		X ⁶
CT or MRI of abdomen and pelvis ⁶	X				X ⁶		X ⁶	X ⁶		X ⁶
TREATMENT EXPOSURE⁷										
mFOLFOX6				X			X			
Nivolumab		B	B	X			X	X		
Vaccination (Arm B ONLY)		B	B	X			X	X		
SPECIMEN COLLECTION										
Tumor Biopsy ⁸	X					X ⁸				
Blood sample for genomic DNA ⁹		B		A						
Blood Samples for correlative research ⁹		B		A	X		X ⁹			
FOLLOW-UP										
Survival Status, Subsequent Therapy										X

CBC with differential to include Hgb, Hct, RBC, WBC, ANC, platelet, MCV and CMP to include sodium, potassium, chloride, creatinine, blood urea nitrogen; liver function tests (LFTs) to include AST, ALT, total bilirubin (direct bilirubin if total is elevated), alkaline phosphatase

Key to Footnotes

1: Medical History. In addition, the following data will be obtained: smoking history questionnaire and a question about how the subject heard about the study. Prior treatment for colon cancer or other malignancies should be noted. If previously treated for colon cancer information regarding diagnosis, staging, treatment, and response should be obtained. Results of prior genomic testing will be requested and are required if available.

2: Physical exams during pre-surgery treatment should be performed on Cycle 1 and Cycle 3. The pre-surgery visit should include evaluation by both the medical and surgical oncologist. Physical exams during post-surgery treatment should be performed on Cycle 5, Cycle 7, Cycle 9, and Cycle 12. During maintenance treatment, physical exams should occur every 28 days (Day 1 of each cycle). Additional physical exams may be performed at the site investigator's discretion. Vital signs to include blood pressure, weight, and height (screening only). Treatment BSA and ECOG performance status should be documented as well.

3: CEA and CA19-9 at screening, prior to surgery, post-surgery Cycle 8 and per Footnote 11.

4: Coagulation studies at screening and prior to surgery, then per investigator's discretion during treatment. Amylase and lipase will be performed at screening and prior to each treatment with nivolumab +/- vaccine. TSH, T3 and T4 to be performed; free versus total T3/T4 is per investigator's discretion at screening, Day -28 (Arm B), Cycle 1, Cycle 3, at the pre-surgery evaluation then monthly. Thyroid testing may be done more frequently at investigator's discretion.

5: For women of childbearing potential (WOCBP): urine or serum β hCG, during screening then within 24 hours of initiation of study drug; only if clinically appropriate. If a urine test is done and it is positive or cannot be confirmed as negative, a serum pregnancy test will be required. WOCBP should be counseled on the importance of initiating birth control procedures from the time of screening and throughout treatment. Please see Section 5.6 for post treatment use of birth control. During treatment, a pregnancy test is required at least 2 days prior to each CV301 dose and every month of Nivolumab treatment. This may be a urine test done at home prior to dosing. Verbal results should be documented.

6: Patients that are registered must have confirmed isolated liver metastases by radiographic imaging. Baseline imaging must include the chest, abdomen, and pelvis by CT, PET/CT or triphasic CT. Re-staging imaging after neoadjuvant therapy to include CT, PET/CT or triphasic CT of the chest, abdomen/pelvis. Additional imaging required for surgical evaluation is at the surgical oncologist's discretion and can include an MRI in addition to restaging scans. Response will be assessed (1) prior to surgery/after 4 cycles of neoadjuvant therapy and (2) at completion of adjuvant therapy. Upon completion of adjuvant therapy, repeat imaging should occur every 3 months during maintenance. After completion of maintenance, imaging should occur every 3 months for 2 years followed by every 6 months for up to an additional year (total 3 years). The modality used for disease evaluation should be consistent throughout the study period.

7: Detailed description of study treatment can be found in Section 5. Arm A is the control arm and Arm B is the experimental arm. Post-surgery therapy will begin when the surgical oncologist deems the patient is ready and is clear of all infectious issues. For those subjects that do not undergo resection, post-surgery therapy may begin at treating physician discretion. The treatment order for Arm A is Nivolumab followed by mFOLFOX6. For Arm B the order of administration is vaccination prior to the start of nivolumab at least one hour prior to mFOLFOX6. A window of +2 days between administration of Nivolumab ± vaccination and mFOLFOX6 will be allowed. This window will accommodate subjects that receive their chemotherapy locally. If there is more than a 2-day delay for any reason, administration of study drugs should be re-aligned so that the chemotherapy falls within +2 days with the next cycle.

8: Required biopsies: Timepoints: (1) pre treatment tumor biopsy and (2) tumor biopsy at surgery or for unresectable subjects a fresh biopsy. The goal of collection is 50 mg of tumor tissue to be used for correlative testing. The site investigator and interventional radiologist should discuss the amount of cores that may be necessary to meet the goal of tissue collection. Testing on tumor tissue obtained pre- and post-therapy to include: PD-1 and PD-L1, mRNA signature by whole transcriptome sequencing using RNAseq TCR clonality assays and Immunoscore via IHC. The pre-treatment biopsy is required regardless of prior biopsy confirmation of metastatic CRC. If the subject does not undergo standard of care surgery after pre-surgery treatment, a research specific biopsy will be performed to obtain tissue for research purposes. There will be a cap of 10 fresh biopsies for unresectable subjects. Genomic testing results are required. FoundationOne platform is preferred, however results from an equivalent genomic platform may be used after discussion with the sponsor investigator. Please see the Correlative Laboratory Manual (CLM) for additional details.

9: Required blood collections: Blood will be collected prior to treatment for genomic DNA testing (Day -28 Arm B and Cycle 1 Day 1 Arm A). Testing on peripheral blood pre-therapy and post-therapy to include: Flow Cytometry, including CEA and MUC-1 antigen-specific immune response, and cytokines and serum soluble factors. Timepoints: (1) before vaccination (Arm B)/treatment (Arm A), (2) before surgery, (3) one month after surgery and (4) six months after surgery. In addition, blood for TCR clonality assays will be collected before vaccination (ARM B)/Treatment (ARM A), and 1 month post-surgery. Please see the Correlative Laboratory Manual (CLM) for additional details.

10. Additional pre-operative testing (such as routine pre-admission testing done prior to elective surgery) may be obtained as per institutional guidelines.

11. Detailed description of study treatment can be found in Section 5. Beginning 4 weeks after completion of adjuvant therapy, patients will continue on maintenance nivolumab but on the standard every 4-week schedule +/- vaccination every 12 weeks. A PE, AE assessment, laboratory assessment, and repeat CEA and CA19-9 will be done prior to each treatment. Additionally, participants will undergo re-staging CT C/A/P every 3 months as per current clinical practice standards. Upon completion of treatment, repeat CT of the C/A/P every 3 months for 2 years followed by every 6 months for up to 1 year (total 3 years).

12: Safety Follow Up: The D30 safety follow-up visit should only occur when subjects permanently stop study treatment for whatever reasons (toxicity, progression, or other reason) and should be performed 30 days (+ 7 days) after the last dose of treatment. Subjects who have an ongoing Grade ≥ 2 or serious AE (SAE) at this visit will continue to be monitored by a member of the study team until the event is resolved, stabilized, determined to be irreversible by the site investigator or a new anti-cancer treatment starts, whichever occurs earlier. The D100 safety follow up visit may be done via phone, email or other avenues as appropriate to assess for SAEs.

13: Upon completion of study treatment, patients should be under surveillance per NCCN guidelines with physical exam (PE), AE assessment, laboratory assessment, and repeat CEA every 3 months for 2 years followed by every 6 months for 1 year (total of 3 years). CT C/A/P will be done every 3 months for 2 years, followed by every 6 months for 1 year (total of 3 years). Colonoscopy at one year with repetition based on findings at the time of the procedure. The above are NCCN guidelines but if not followed, do not constitute a deviation from the protocol. Treating staff should monitor according to standard of care for patients receiving immunotherapy medications. If a patient progresses information regarding disease recurrence, anti-cancer treatment and response will be obtained. This may be done via phone call, email or other avenues as appropriate.

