STUDY DESIGN	
This is a multi-center Phase II randomized study. We plan to enroll 78 patients with biopsy-proven hepatic-limited metastatic colorectal cancer deemed resectable after multi-disciplinary discussion. Eligible patients must have confirmed isolated liver metastases by radiographic imaging of the investigators' choosing. Imaging must include the chest, abdomen, and pelvis regardless of imaging modality chosen. Patients will be randomized to either the control arm or the experimental arm. The control arm will receive mFOLFOX6 every 2 weeks for 4 cycles concurrently with Nivolumab. The experimental arm will first be treated with 2 vaccinations of MVA-BN-CV301 given two weeks apart (Days -28, -14) concurrently with Nivolumab followed by 4 vaccinations of FPV-CV301 given two weeks apart concurrently with mFOLFOX6 and Nivolumab, which will again be administered every 2 weeks for 4 cycles (FPV-CV301, mFOLFOX6 and Nivolumab) After Cycle 4, patients will be re-evaluated for surgical resection by re-staging CT chest, abdomen and pelvis (C/A/P). Patients still considered resectable will undergo surgical resection with the goal of complete resection. Patients who cannot be completely resected will continue to be followed on study, and an additional appropriate candidate will be randomized to the corresponding arm.
 
We will collect peripheral blood and tumor tissue at the time of surgical resection, if applicable, or by re-biopsy if resection is not possible. Post-operative therapy will begin when patients are deemed ready by their surgical oncologist team. Patients in the control arm will then undergo another 8 cycles of mFOLFOX6 with Nivolumab administered concurrently. Nivolumab will then be administered every four weeks. The experimental arm will receive the same post-operative regimen but including FPV-CV301 boosters given concurrently with mFOLFOX6 and Nivolumab. FPV-CV301 will then be administered every 12 weeks, and Nivolumab every 4 weeks. We will collect peripheral blood for evaluation of correlates upon the completion of therapy. The vaccination approach of initial immunization during the neoadjuvant period followed by FPV-CV301 boosters for two years postoperatively was chosen to optimize the induction of a long-lasting tumor-specific host response.

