11.2 Reporting

11.2.1 Adverse Events

- AEs will be recorded from time of signed informed consent until 100 days after discontinuation of study drug(s) or until a new anti-cancer treatment starts, whichever occurs first.
- AEs will be recorded regardless of whether or not they are considered related to the study drug(s).
- All AEs will be recorded in the subject's medical record and on the appropriate study specific eCRF form within the EDC system.
- AEs considered related to study drug(s) will be followed until resolution to \leq Grade 1 or baseline, deemed clinically insignificant, and/or until a new anti-cancer treatment starts, whichever occurs first.

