11.2.2 Serious Adverse Events (SAEs)

11.2.2.1 Site Requirements for Reporting SAEs to HCRN

- SAEs will be reported from time of signed informed consent until 100 days after discontinuation of study drug(s) or until a new anti-cancer treatment starts, whichever occurs first.

- SAEs will be reported on the SAE Submission Form **within 1 business day** of discovery of the event.
- SAEs include events related and unrelated to the study drug(s).
- All SAEs will be recorded in the subject's medical record and on the appropriate study specific eCRF form within The EDC system.
- All SAEs regardless of relation to study drug will be followed until resolution to \leq Grade 1 or baseline and/or deemed clinically insignificant and/or until a new anti-cancer treatment starts, whichever occurs first.

The site will submit the completed SAE Submission Form to HCRN **within 1 business day** of discovery of the event. The form may be submitted to HCRN electronically to [contact]. The site investigator is responsible for informing the IRB and/or other local regulatory bodies as per local requirements.

The original copy of the SAE Submission Form and the email correspondence must be kept within the study file at the study site.

Once the SAE has resolved (see resolution guidelines listed in 11.2.2.1), sites must submit a follow-up SAE Submission Form within a reasonable timeframe to HCRN electronically to [contact].

11.2.2.2 HCRN Requirements for Reporting SAEs to Bavarian Nordic and Bristol Myers Squibb (BMS)

HCRN will report all SAEs to Bavarian Nordic (BN) at [contact] and BMS at [contact] **within 1 business day** of receipt of the SAE Submission Form from a site. Follow-up information will be provided to Bavarian Nordic and BMS **within 1 business day** as it is received from site.

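### Adverse events are assessed for three years after treatment, but AE recording and SAE reporting stop at day 100, so a related event that begins later falls outside both

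*Combined protocol and SAP*

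**What the plan says.** In Section 7, the calendar row "AEs & concomitant medications" is marked in the Follow-up column, which is separate from the column for the D30 and D100 safety visits. Footnote 13 describes that follow-up: "patients should be under surveillance per NCCN guidelines with physical exam (PE), AE assessment, laboratory assessment", with the interval given as "repeat CEA every 3 months for 2 years followed by every 6 months for 1 year (total of 3 years". It then qualifies the schedule: "The above are NCCN guidelines but if not followed, do not constitute a deviation from the protocol". It also asks staff to monitor by the standard of care for patients on immunotherapy.

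Section 11.2.1 states: "AEs will be recorded from time of signed informed consent until 100 days after discontinuation of study drug(s". Section 11.2.2.1 states: "SAEs will be reported from time of signed informed consent until 100 days after discontinuation of study drug(s". Both periods end earlier if a new anti-cancer treatment starts.

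Events already open are treated differently. Section 11.2.1 says "AEs considered related to study drug(s) will be followed until resolution", and 11.2.2.1 has a similar rule for every SAE whatever its cause. Neither rule has a day-100 limit, although both stop at new anti-cancer treatment. Footnote 12 keeps Grade 2 or higher AEs and SAEs that are ongoing at the D30 visit under observation.

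The synopsis says the booster schedule was "chosen to optimize the induction of a long-lasting tumor-specific host response". Section 6.2 provides for an autoimmune response to CV301 that causes an SAE. Section 12.5 defines who is evaluable for toxicity but gives no time window.

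**The concern.** The calendar asks sites to look for adverse events for three years, while the reporting section stops collecting new ones after about three months. Nothing says what a site should do with an event that begins between day 100 and the end of follow-up. If the investigator thinks the event was caused by the vaccine or by nivolumab, no rule carries it to the case report form, to the two drug suppliers (11.2.2.2) or to the monitoring committee's adverse event summary (13.2).

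Two things are at stake. The first is the late safety record of a regimen intended to produce a durable immune response, in patients treated with a chance of cure. The second is consistency. One site may enter late events because the calendar marks them, while another leaves them out because 11.2 has closed. The documents describe no placebo, so reporting left to discretion could also differ between the arms.

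**Working it through.** **Inputs.** Visit intervals and three-year total: footnote 13. Follow-up visit window of ±14 days: calendar. End of recording at 100 days: 11.2.1 and 11.2.2.1. Treatment durations: 5.1.2 to 5.1.5. Enrolment of 12 months and study duration of 60 months, both estimates: synopsis.

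**1. The plan's own figure.** 24/3 = 8 visits in the first two years and 12/6 = 2 in the third. 8 × 3 + 2 × 6 = 36 months, which reproduces the stated three years. The 10 visits fall at months 3, 6, 9, 12, 15, 18, 21, 24, 30 and 36.

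**2. Visits against day 100.** Day = month × 365.25/12, counted from the end of study drug.

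| Assumption | Month 3 | Month 6 | Month 36 | By day 100 | After day 100 |
|---|---|---|---|---|---|
| Nominal date | 91 | 183 | 1096 | 1 | 9 |
| 14 days early | 77 | 169 | 1082 | 1 | 9 |
| 14 days late | 105 | 197 | 1110 | 0 | 10 |
| 28-day months | 84 | 168 | 1008 | 1 | 9 |

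**3. Share of follow-up inside the period.** 100/(3 × 365.25) = 100/1095.75 = 9.1%. The remaining 1095.75 − 100 = about 996 days have no rule for a new event. A patient who starts new anti-cancer treatment before month 3 has no follow-up visit inside the period.

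**4. What the period does cover.** Recording starts at consent, so it includes all of treatment. For an Arm B patient who completes everything, the approximate weeks are 4 (Day −28 to Cycle 1) + 8 (Cycles 1–4) + 4 (to surgery) + 7 (midpoint of 6–8 weeks' recovery) + 16 (Cycles 5–12) + 4 (gap) + 96 (24 four-week cycles) = 139 weeks, or about 2.7 years. The 100 days come on top. Arm A is about 4 weeks shorter.

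**5. How much follow-up the study length allows.** 139 weeks is about 32 months. With the 60-month estimate, the first completer enrolled has about 60 − 32 = 28 months after treatment, and the last about 60 − 12 − 32 = 16 months. These allow 8 and 5 nominal visits, of which 7 and 4 fall after day 100.

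**6. The passages side by side.**

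| Event | Assessed at follow-up? | Recorded or reported under 11.2? |
|---|---|---|
| Related AE, or any SAE, that began by day 100 and is still open | Yes | Yes; followed to resolution |
| Related SAE that begins after day 100 | Yes | Outside the period |
| Other AE that begins after day 100 | Yes | Outside the period |

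The test is the date of onset. An event found at month 6 that began before day 100 still belongs in the record.

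**The case against.** The strongest reply is that the two places can be read together. Open related AEs and all open SAEs are tracked with no day-100 limit, so the follow-up mark has an ordinary use: checking on events already recorded. Day 100 is also stated consistently in both parts of 11.2 and in the D100 contact, which suggests a deliberate choice. The ten visits are guideline surveillance, and missing them is not a deviation. Deaths after day 100 are still seen through survival status.

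Most of this stands. It does not settle the matter, because neither the calendar nor footnote 13 limits AE assessment to ongoing events, and no passage says what happens to a new one. The no-deviation sentence makes late capture less uniform, but it does not say which rule applies when a late event is found.

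Three stronger readings are tempting, and the documents do not support them.

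- A reader might infer that nothing seen after day 100 can enter the safety data. The rules on following open events contradict this.
- A reader might infer that the trial could never show late autoimmune toxicity. Recording runs through more than two years of treatment for completers, so harm that emerges a year or more after the first vaccination is captured. Section 6.3.4 does not help that reading either: its late endocrine events occur while patients are still on treatment.
- A reader might try to count the events that would be lost. The documents give no rate of late related events. Three full years of follow-up for all 70 resected patients would overstate the time at risk, given the 22 expected deaths (12.8), the cut-off at new anti-cancer treatment and the 60-month study estimate.

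**Conclusion.** The conflict is real but narrow. It concerns events that begin after day 100, above all SAEs judged related to CV301 or nivolumab. On nominal dates 9 of the 10 follow-up assessments lie outside the recording and reporting period, and all 10 do if month 3 is late in its window. The period covers about 9% of the three-year follow-up. On the estimated study length completers would have fewer visits, but most would still lie outside (4 of 5 to 7 of 8).

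The visit count assumes that the footnote 13 schedule is followed, that its clock starts at the end of study drug, and that recording is not cut short by new anti-cancer treatment. The number of events affected cannot be derived from the documents. The primary survival analysis is untouched. The correction should be made because it is cheap, and because without it the late safety data depend on which section a site reads.

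**What to change.** Reconcile Section 7 with 11.2 in one of two ways.

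- **Preferred.** Keep day 100 for all-cause events. Add to 11.2.1 and 11.2.2.1 that SAEs with onset after day 100 which the investigator considers related to CV301 or nivolumab, learned of at existing follow-up contacts, are recorded and reported. Say whether this also holds after new anti-cancer treatment has started. In Section 12, summarise these by arm as late events in the Treated set, separately from events within the period.
- **Alternative.** Limit the follow-up AE entry in the calendar and footnote 13 to events already ongoing, and state that late-onset toxicity is not collected, so that no one reads its absence as evidence of safety.

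The preferred option takes about two sentences in 11.2 and one in Section 12. It uses existing contacts and forms and changes no treatment. Its cost is a few more late reports, with attribution less certain so long after the last dose. The summary should also state that ascertainment after day 100 rests on guideline surveillance and may be incomplete.
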